3. STUDY DESIGN

3.1. Study Overview

This is a Phase 1, open label, multi-center, multiple dose, safety, PK, PD and immunogenicity study evaluating the components of VBIR-2 (PF-06936308), now solely in participants with advanced or metastatic NSCLC or TNBC.

The study is divided into two parts, Dose Escalation (Part 1) in participants with NSCLC and TNBC without acceptable alternative treatment options, followed by Dose Expansion (Part 2) in participants with NSCLC who have progressed on or after treatment with platinum-based chemotherapy and treatment with ≤ 1 immune checkpoint inhibitor, given concurrently or sequentially with chemotherapy.

Dose Escalation (Part 1)

The Dose Escalation (Part 1) completed its determination of MTD after 6 cohorts. It enrolled 36 participants in Part 1. It included participants for whom no standard therapy was available for advanced or metastatic NSCLC or TNBC, without restrictions as to the prior number of lines of immunotherapy or chemotherapy.

Six dose escalation cohorts were investigated:

- AdC68 2×10^{11} VP +5 mg pDNA.
- AdC68 6×10^{11} VP +5 mg pDNA:
 - If needed – dose reduction of the AdC68 dose to 2×10^{11} VP is allowed.
 - AdC68 6×10^{11} VP +5 mg pDNA +40 mg tremelimumab.*
 - AdC68 6×10^{11} VP +5 mg pDNA +40 mg tremelimumab +130 mg sasanlimab*;
 - AdC68 6×10^{11} VP +5 mg pDNA +40 mg tremelimumab +300 mg sasanlimab;

- AdC68 6×10^{11} VP +5 mg pDNA +80 mg tremelimumab +300 mg sasanlimab.*
* If needed – dose reduction of the tremelimumab or sasanlimab dose is allowed.

3.1.1. Criteria for Dose Escalation

The principles of modified toxicity probability interval (mTPI) design,¹⁴⁰ will be utilized for the dose escalation portion of the study.

An mTPI design, targeting a DLT rate of 27.5% and an acceptable DLT equivalence interval (22.5% to 32.5%), will be utilized in the dose escalation phase.

The dose levels to be evaluated are given in [Figure 1](#). If a high DLT rate is observed at the starting dose, the study may explore a lower dose or may be stopped.

Each cohort would enroll 2 to 4 DLT evaluable participants and at least 6 and up to 12 participants would be enrolled at a dose level that is predicted to be the MTD as per the mTPI method. Dose cohorts with an acceptable safety profile may be expanded up to N=12 to further assess safety, [CCI](#) pharmacokinetics, [CCI](#).

Decisions to enroll additional participants at dose levels already cleared for safety will be based on clinical judgment.

The mTPI method relies upon a statistical probability algorithm, calculated using all participants treated in the current dose level to determine one of the following dose-finding decisions: the subsequent dose should be escalated, maintained at the current dose, or de-escalated in the next cohort of 2 to 4 participants, or the trial should be terminated. It is currently envisaged that AdC68 6×10^{11} VP +5 mg pDNA +150 mg tremelimumab +300 mg ANTI-PD-1 (PF-06801591) will potentially be the highest dose level.

Table 3. Decision Rules

Number of participants treated at current dose

#DLTs	1	2	3	4	5	6	7	8	9	10	11	12
0	E	E	E	E	E	E	E	E	E	E	E	E
1	D	S	S	S	E	E	E	E	E	E	E	E
2		U	D	S	S	S	S	S	S	E	E	E
3			U	U	D	D	S	S	S	S	S	S
4				U	U	U	U	D	S	S	S	S
5					U	U	U	U	U	D	S	S
6						U	U	U	U	U	U	U

- Columns indicate number of participants in the cohort and rows indicate number of participants with DLTs
- E= Escalate to the next higher dose; S: Stay at the same dose; D: De-escalate to the previous lower dose; U: De-escalate to the previous lower dose and the current dose will never be used again in the trial

If a participant discontinues close to Day 28 for reasons other than toxicity and due to an evident non drug-related event, the participant may be deemed evaluable for safety if safety assessments have been unremarkable and the investigator and sponsor's medical monitor both agree that the participant is evaluable for DLT safety observation.

The dose escalation Part 1 of the study will stop if any of the following criteria is met:

The maximum sample size has been achieved (approximately 36 participants in total as per the current dosing schedule);

6 to 12 participants have been enrolled at a dose level that is predicted to be the MTD according to [Table 3](#);

All dose levels explored appear to be overly toxic, and the MTD cannot be determined;

All candidate dose levels have been tested and deemed safe.

As an example, if the total number of participants (cumulative in the study) treated at the current dose is 4, the following dosing rules are applied:

0-1 DLT -> escalate;

1 DLT -> remain at the same dose;

2 DLTs -> De-escalate to the previous or intermediate lower dose;

3-4 DLTs -> De-escalate and consider current dose as intolerable.

Activation of each cohort will occur no sooner than 28 days after the first 2-4 participants receive the first AdC68 vaccination, but may occur later if the sponsor and investigators determine additional safety data is needed. The Pfizer clinical team and investigators will review all available safety data from the previous and current cohorts prior to making a decision to dose escalate. If no safety issues that would prohibit dose escalating are observed, the next cohort of participants would be open for accrual.

If dose escalation continues up to a predefined Maximum Feasible Dose (MFD), the escalation is halted without a maximum tolerated dose (MTD) estimate. In those circumstances, the MFD may be the recommended Phase 2 dose (RP2D).

3.1.2. Dose Expansion (Part 2)

The Expansion Phase will enroll participants in 1 cohort of participants with metastatic or locally-advanced NSCLC who have previously received treatment with a platinum-based chemotherapy regimen and not more than one treatment with an immune checkpoint inhibitor regimen either concurrently or sequentially with the chemotherapy.

Participants will participate in the active treatment period of the study for approximately 9 months. This includes a 28 day screening period followed by 2 cycles of vaccine treatment, totaling 8 months in duration. After completion of the active treatment phase (vaccine prime, pDNA boosts, checkpoint inhibitor support), participants will then enter the maintenance phase of the study (pDNA boosts only with checkpoint inhibitor support).

[figure not shown]
Treatment will continue until: disease progression, unacceptable toxicity, death or participant's or investigator's decision occurs. Since the treatment effect of cancer immunotherapy can often be delayed, participants will be encouraged to continue on study treatment for at least 24 weeks before an investigator considers removing the participant due to disease progression, as long as (a) Participant and investigator agree; (b) Participant continues to meet all other study protocol eligibility criteria; (c) Toxicity remains acceptable; and (d) No deterioration of participant performance status. Disease progression will be confirmed with 2 consecutive timepoints at least 4-8 weeks apart in the absence of rapid clinical deterioration.

Participants who demonstrate clinical benefit with manageable toxicity and who are willing to continue receiving study treatment will be given the opportunity to continue treatment upon agreement between the investigator and sponsor. When the participant discontinues treatment, they will then enter a 6 month post-dose follow-up period to assess safety CCI

The end of the study is the last participant last visit.

The overall design is presented in Figure 1 below:

Figure 1. Study Design

3.2. DLT Definition

Severity of adverse events (AEs) will be graded according to Common Terminology Criteria for Adverse Events (CTCAE) version 5.0. For the purpose of dose escalation, any of the following AEs occurring in the first 28 days following the first AdC68 vaccination that are considered possibly related to study treatment and are not considered related to disease/progression will be classified as DLTs:

Hematologic:

- Grade ≥ 3 neutropenia lasting > 7 days.
- Febrile neutropenia (febrile neutropenia is defined as an absolute neutrophil count $< 1.0 \times 10^9/L$ with a single temperature of $> 38.3^{\circ}\text{C}$, or 101°F , or a sustained temperature of $\geq 38^{\circ}\text{C}$, or 100.4°F , for more than one hour).
- Grade ≥ 3 neutropenic infection.
- Grade ≥ 3 thrombocytopenia with \geq Grade 2 clinically significant bleeding (for bleeding events with no grading available, clinically significant bleeding is defined as requiring hospitalization or urgent medical intervention).
- Grade ≥ 3 anemia lasting more than 7 days.
- Grade ≥ 3 lymphopenia lasting more than 14 days.

Nonhematologic:

- Grade ≥ 3 AEs that are considered non-hematologic, non-hepatic major organ toxicity (excluding alopecia of any grade; Grade 3 nausea/vomiting or diarrhea < 72 hours with adequate antiemetic and other supportive care; \geq Grade 3 electrolyte abnormality that lasts < 24 to 72 hours, is not clinically complicated, and resolves spontaneously or responds to conventional medical interventions).
- Grade 3 flu-like symptoms lasting greater than 3 days with adequate treatment.
- Fever of $> 40.0^{\circ}\text{C}$, or 104.0°F , lasting for more than 3 days with adequate treatment.
- Concurrent aspartate aminotransferase (AST) or alanine aminotransferase (ALT) > 3 upper limit of normal (ULN) and total bilirubin > 2 ULN (potential Hy's law case).
- Nonhematologic laboratory abnormalities: Grade ≥ 3 laboratory abnormalities either associated with symptoms or associated with worsening of an existing condition or that suggests a new disease process or that requires additional active management (eg, discontinuation of the drug, close observation, more frequent follow-up)

assessments, further diagnostic investigation or specific treatment). In addition, clinically important or persistent toxicities that are not included in the above criteria may be considered a DLT following review by Pfizer and the investigators. All DLTs need to represent a clinically significant shift from baseline.

The following AEs will not be adjudicated as DLTs:

- Isolated Grade 3 laboratory abnormalities that are not associated with clinical sequelae and are corrected with supplementation/appropriate management within 72 hours of onset.

3.3. MTD Definition

The MTD is defined as the highest dose with true toxicity probabilities in the equivalence interval (EI) where the EI is defined as (22.5%, 32.5%).

Even though the mTPI model may select an MTD with an incidence of DLTs that is higher than 32.5% since mTPI decision rules are based on unit probability mass (UPM) and not on point estimates of the DLT rate (see [Section 9.2.1](#)), doses with an incidence of DLT >32.5% (eg, 3 out of 9) cannot be declared as the MTD. In practice, model recommendations may be overridden by clinical judgment, and MTD with an incidence of DLTs that is higher than 32.5% will not be considered acceptable to be selected as MTD.

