Decision rules are based on calculating posterior probabilities of 3 dosing intervals corresponding to under, proper, and over dosing in terms of toxicity. Specifically, the underdosing interval is defined as $(0; pT - e_1)$, the over-dosing interval $(pT + e_2, 1)$, and the proper-dosing interval $(pT - e_1, pT + e_2)$, where e_1 and e_2 are small fractions. In this study, e_1 is selected as 0.05 and e_2 is selected as 0.05, therefore, the target interval for the DLT rate is $(0.225, 0.325)$. The 27.5% target, the symmetry of the Equivalence Interval, and its upper limit were chosen based on safety considerations. The prior distribution of DLT is set as a beta $(0.5, 0.5)$, and the threshold probability for early termination and dose exclusion is set to 0.95. Even though the upper limit of the mTPI is higher than 27.5%, doses with an incidence of DLT $>27.5\%$ (eg, 3 out of 9) cannot be declared as the MTD.

The 3 dosing intervals are associated with 3 different dose-escalation decisions. The underdosing interval corresponds to a dose-escalation I, overdosing corresponds to a dose de-escalation (D/U), and proper dosing corresponds to remaining at the current dose (S).

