9.2.2. Statistical Method for Estimating the MTD

As previously described, the estimated MTD is the highest tested dose level with a DLT rate $\leq 32.5\%$ in at least 6 DLT-evaluable participants. It is assumed that higher doses result in higher toxicity rates. But, due to the relatively low number of participants that may be potentially allocated to any dose combination, this assumption may be incorrect, allowing for higher dose levels to be tested.

Clinical judgment will be exercised in taking forward doses to the expansion cohort(s), in case no clear choice exists between more than 1 competing MTD. This decision will be based upon the combination of data related to safety, anti-tumor activity, and clinical judgment of the investigators and the sponsor.

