2. INTRODUCTION

PF-06936308 is a vaccine-based immunotherapy regimen-2 (VBIR-2) that is currently being investigated in patients with advanced non-small cell lung cancer (NSCLC) and metastatic triple-negative breast cancer (mTNBC). The protocol C3621001 outlines the VBIR-2 study for Part 1 (dose escalation).

This document describes the planned statistical analyses for Protocol C3621001, dated 16 March 2018. This SAP is meant to supplement the study protocol. This SAP supersedes the statistical considerations identified in the protocol and, where considerations are substantially different they will be identified as such. Any deviations from this analysis plan will be described in the clinical study report (CSR). Any post-hoc, or unplanned analyses performed that are not specified in this SAP will be clearly identified in the CSR. This plan is developed and finalized prior to database lock of the clinical database. This SAP is written with consideration of the recommendations outlined in the International Conference on Harmonisation (ICH) E9 Guideline (Guidance for Industry: Statistical Principles for Clinical Trials) and on the ICH E3 Guideline (Guidance for Industry: Structure and Content of Clinical Study Reports).

Note: in this document any text taken directly from the protocol is *italicized*.

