2.1.2. Criteria for Dose Escalation

The principles of modified toxicity probability interval (mTPI) design (Ji et al., 2010)4, will be utilized for the dose escalation portion of the study.

An mTPI design, targeting a DLT rate of 27.5% and an acceptable DLT equivalence interval (22.5% to 32.5%), will be utilized in the dose escalation phase.

The dose levels to be evaluated are given in Section 2.1.1 in the protocol. If a high DLT rate is observed at the starting dose, the study may explore a lower dose or may be stopped.

Each cohort would enroll 2 to 4 DLT evaluable patients and at least 6 and up to 12 patients would be enrolled at a dose level that is predicted to be the MTD as per the mTPI method. Dose cohorts with an acceptable safety profile may be expanded up to $N=12$ to further assess safety, CCI [REDACTED] pharmacokinetics, CCI [REDACTED]. Decisions to enroll additional patients at dose levels already cleared for safety will be based on clinical judgment.

The mTPI method relies upon a statistical probability algorithm, calculated using all patients treated in the current dose level to determine one of the following dose-finding decisions: the subsequent dose should be escalated, maintained at the current dose, or de-escalated in the next cohort of 2 to 4 patients, or the trial should be terminated. It is currently envisaged that $AdC68 6 \times 10^{11} VP + 5 \text{ mg pDNA} + 150 \text{ mg tremelimumab} + 300 \text{ mg ANTI-PD-1 (PF-06801591)}$ will be RP2D.

Decision rules are based on calculating posterior probabilities of 3 dosing intervals corresponding to under, proper, and over dosing in terms of toxicity. Specifically, the underdosing interval is defined as $(0; pT-e1)$, the over-dosing interval $(pT+e2, 1)$, and the proper-dosing interval $(pT- e1, pT+ e2)$, where $e1$ and $e2$ are small fractions. In study, $e1$ is

selected as 0.05 and e_2 is selected as 0.05, therefore, the target interval for the DLT rate is (0.225, 0.325). The 27.5% target, the symmetry of the Equivalence Interval and its upper limit were chosen based on safety considerations. The prior distribution of DLT is set as a beta (0.5, 0.5), and the threshold probability for early termination and dose exclusion is set to 0.95. Even though the upper limit of the mTPI is higher than 27.5%, doses with an incidence of DLT > 27.5% (eg, 3 out of 9) cannot be declared as the MTD.

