2.1.4. MTD Definition

The MTD is defined as the highest dose with true toxicity probabilities in the equivalence interval (EI) where the EI is defined as (22.5%, 32.5%).

Even though the mTPI model may select an MTD with an incidence of DLTs that is higher than 32.5% since mTPI decision rules are based on unit probability mass (UPM) and not on point estimates of the DLT rate (see Section 9.2.1), doses with an incidence of DLT >32.5% (eg, 3 out of 9) cannot be declared as the MTD. In practice, model recommendations may be overridden by clinical judgment, and MTD with an incidence of DLTs that is higher than 32.5% will not be considered acceptable to be selected as MTD.

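### Protocol 9.2.2 accepts an MTD with up to 32.5% observed DLTs while 9.2.1 bars anything above 27.5%; separately, the four-participant example and the 2/10 table cell depart from the stated escalation rule

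*Protocol*

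**What the plan says.** **Ceiling on the observed rate, Protocol.** Section 3.3 states that "doses with an incidence of DLT >32.5% (eg, 3 out of 9) cannot be declared as the MTD". Section 9.2.2 puts the same figure as a rule for acceptance: "the estimated MTD is the highest tested dose level with a DLT rate" of at most 32.5%, in six or more DLT-evaluable participants. Section 9.2.1 uses a lower figure: "Even though the upper limit of the mTPI is higher than 27.5%, doses with an incidence of DLT" above 27.5% cannot be named the MTD.

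**Ceiling, SAP.** Section 2.1.2 says "doses with an incidence of DLT > 27.5% (eg, 3 out of 9) cannot be declared as the MTD". Section 2.1.4 repeats the sentence from Protocol 3.3 and adds "MTD with an incidence of DLTs that is higher than 32.5% will not be considered acceptable to be selected as MTD". The SAP introduction says "This SAP supersedes the statistical considerations identified in the protocol".

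**Escalation rule.** Protocol 9.2.1 and SAP 2.1.2 specify mTPI with target 27.5%, margins of 0.05 on each side, a Beta(0.5, 0.5) prior and an exclusion threshold of 0.95. Protocol Table 3 and SAP Table 1 print the same decisions. Both documents also give a worked example for four participants at a dose:

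| DLTs among 4 | Protocol 3.1.1 example | SAP 2.1.2 example | Both tables |
|---|---|---|---|
| 0 | Escalate | Escalate | Escalate |
| 1 | Escalate on one line, remain on the next | Remain | Stay |
| 2 | De-escalate | De-escalate | Stay |
| 3 or 4 | De-escalate, dose intolerable | De-escalate, dose intolerable | De-escalate, never reuse |

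**Status.** Protocol 3.1 reports that Part 1 "completed its determination of MTD after 6 cohorts. It enrolled 36 participants in Part 1".

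**The concern.** Estimating the MTD is a primary objective of Part 1. A dose whose observed rate lies above 27.5% and at or below 32.5% qualifies under Protocol 9.2.2 and is barred by 9.2.1. The illustration attached to both ceilings, 3 out of 9, is 33.3%. It exceeds both and so does not show which one governs.

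The escalation slips are a separate matter and do not bear on the ceiling. If a cohort passed through 1/4, 2/4 or 2/10, a reader of the study report cannot tell from the documents which action the plan required, or whether the printed action is the one that the stated model produces.

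Since escalation is over, what is at stake is whether the report can show that the declared MTD met a rule fixed in advance.

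**Working it through.** **1. Where the two ceilings disagree.** Inputs: 27.5% (Protocol 9.2.1), 32.5% (Protocol 9.2.2), and 6 to 12 participants at the predicted MTD (Protocol 3.1.1). A clash needs a whole number x with 0.275n < x ≤ 0.325n.

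| n | 0.275n | 0.325n | x in range |
|---|---|---|---|
| 6 | 1.650 | 1.950 | none |
| 7 | 1.925 | 2.275 | 2 (28.6%) |
| 8 | 2.200 | 2.600 | none |
| 9 | 2.475 | 2.925 | none |
| 10 | 2.750 | 3.250 | 3 (30.0%) |
| 11 | 3.025 | 3.575 | none |
| 12 | 3.300 | 3.900 | none |

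**2. The decision table.** Inputs: Beta(0.5, 0.5) prior and intervals (0, 0.225), (0.225, 0.325) and (0.325, 1). With x DLTs in n, let F be the distribution function of Beta(0.5 + x, 0.5 + n − x). The unit probability mass of an interval (a, b) is [F(b) − F(a)] / (b − a). The largest of the three gives Escalate, Stay or De-escalate. The dose is excluded if P(rate > 0.275) > 0.95.

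Of the 69 printed cells, 68 reproduce. The one mismatch is 2/10.

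| x/n | Under | Proper | Over | Computed | Printed |
|---|---|---|---|---|---|
| 2/9 | 2.119 | 2.579 | 0.393 | Stay | Stay |
| 2/10 | 2.426 | 2.503 | 0.302 | Stay | Escalate |
| 2/11 | 2.706 | 2.362 | 0.230 | Escalate | Escalate |
| 1/4 | 1.809 | 1.906 | 0.596 | Stay | Stay |
| 2/4 | 0.446 | 1.203 | 1.154 | Stay | Stay |
| 2/7 | 1.443 | 2.429 | 0.641 | Stay | Stay |
| 3/10 | 1.198 | 2.808 | 0.666 | Stay | Stay |

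At 3/4 and 4/4, P(rate > 0.275) is 0.978 and 0.999, so exclusion is right there. The four-participant example is therefore wrong at 2 DLTs in both documents. The Protocol's version is also wrong on the first of its two lines for 1 DLT.

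A coarse search over the prior, target and margins found that the whole printed table reproduces if, for example, the lower margin is 0.04 instead of 0.05. That is not the stated value, and nothing shows that it was used.

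**3. Size of the ceiling clash, conditionally.** If the level closes at exactly n = 7, P(x = 2) = 21p²(1 − p)⁵. If it closes at exactly n = 10, P(x = 3) = 120p³(1 − p)⁷.

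| True rate p | P(2/7) | P(3/10) |
|---|---|---|
| 0.225 | 0.297 | 0.230 |
| 0.275 | 0.318 | 0.263 |
| 0.325 | 0.311 | 0.263 |

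These hold only given that final n. With cohorts of 2 to 4, reaching 7 needs mixed sizes (3 and 4, or 2, 2 and 3), and reaching 10 needs all twos or mixed sizes. Protocol 3.1.1 also allows a level to be expanded up to 12 on clinical judgment, not necessarily in whole cohorts, so neither total can be ruled out. An unconditional probability would need dose-toxicity curves, cohort sizes and a stopping habit that the documents do not give, so none is offered.

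**The case against.** **The SAP does not clash with itself.** A reader might infer that the SAP, too, both allows and bars 2/7 and 3/10. It does not. Its two sentences are both prohibitions and are met together by applying 27.5%. The 22.5% to 32.5% interval in its MTD definition concerns true toxicity probabilities, not observed rates. This stands, and the direct conflict is confined to Protocol 9.2.1 against 9.2.2. The SAP's claim to supersede the Protocol does not close the matter, because it carries both figures without saying that 27.5% is meant to govern.

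**It looks like an editing slip.** Protocol 3.3 refers the reader to 9.2.1, the sentences are nearly identical, and 9.2.2 presents 32.5% as a restatement. That makes 32.5% a plausible intent. It does not make it a rule fixed in advance, and 27.5% is the reading that satisfies every sentence.

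**The table is what was applied.** Protocol 9.2.1 describes decisions as calculated in advance and tabulated, and both tables agree at 2/10. An observed 20% lies below the interval, so Escalate is not unreasonable there. The four-participant list is only an example, and at 2/4 it is the more cautious action. All of this is fair and is why errata are enough.

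**Clinical judgment may override the model.** Protocol 3.3 says so, but restates the 32.5% bar in the same sentence. It does not choose between the ceilings.

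**Conclusion.** The Protocol contradicts itself on the ceiling for declaring the MTD. For 6 to 12 evaluable participants, the conflict is limited to 2/7 and 3/10. At every other count in that range, the two ceilings give the same answer. Given closure at n = 7 or n = 10, the clash count has a probability of about 30% to 32% or 23% to 26% at the true rates tabulated.

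The four-participant example is wrong at 2 DLTs in both documents (1.203 against 1.154), and the Protocol's version contradicts itself at 1 DLT. The 2/10 cell does not follow from the stated prior and interval (2.503 against 2.426). Both model comparisons are near ties.

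A reader might go further and infer that the MTD was wrongly declared, that a cohort was wrongly escalated, or that the Part 2 dose is unsafe. The documents do not support this. Part 1 is complete, no DLT counts are visible, and Protocol 3.5 allows the recommended dose to lie below the MTD. The finding is about traceability of a primary objective.

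**What to change.** Correct the Protocol and the SAP together. The direct conflict sits in the Protocol, and Protocol section 9 requires major changes to primary-endpoint analyses to appear in a protocol amendment. The SAP says "This plan is developed and finalized prior to database lock of the clinical database", so it can still be amended if lock has not occurred. If it has, put the same statement in the clinical study report.

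1. Name one ceiling on the observed DLT rate and disclose that it was settled after Part 1.
2. Do not rely on the laxer figure alone. Report DLTs over evaluable participants at the declared MTD against both 27.5% and 32.5%. Do so with and without late-onset toxicities, which SAP 2.1.5 counts toward the MTD and which could change the fraction.
3. If the count is 2/7 or 3/10, say that the dose meets Protocol 9.2.2 and fails 9.2.1.
4. Record the four-participant example and the 2/10 cell as errata. State which rule was applied in Part 1 and whether any cohort reached 1/4, 2/4 or 2/10.
5. Do not present a corrected table as if it had governed Part 1. For any further escalation, use 0 escalate, 1 or 2 stay, 3 or 4 de-escalate and exclude at n = 4, and Stay at 2/10.

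The cost is one paragraph in each document, a short errata note and a few sentences in the report, using counts that the sponsor already holds. No new data are needed.
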